	Grade 3	
Grade 3
 
 • Hold study drug/study regimen dose until resolution to Grade ≤ 1. • Permanently discontinue study drug/study regimen if Grade 3 imAE does not resolve to Grade ≤ 1 within 30 days or if there are signs of respiratory insufficiency. 	
For Grade 3 or 4
 
 - Monitor symptoms closely; recommend hospitalization. - Consider Rheumatology and/or Neurology consult. - Consider discussing with the Clinical Study Lead, as needed. - Promptly start IV methylprednisolone 2 to 4 mg/kg/day systemic steroids along with receiving input from Neurology consultant. - If after start of IV methylprednisolone at 2 to 4 mg/kg/day there is no improvement within 2 to 3 days, consider starting another immunosuppressive therapy such as a TNF inhibitor (e.g., infliximab at 5 mg/kg IV, may be repeated at 2 and 6 weeks after initial dose at the discretion of the treating provider or relevant practice guidelines). Caution: It is important to rule out sepsis and refer to infliximab label for general guidance before using infliximab. - Consider whether patient may require IV IG, plasmapheresis.

	Grade 4	For Grade 4 Permanently discontinue study drug/study regimen	Grade 4 – Monitor symptoms closely; recommend hospitalization. – Consider Rheumatology and/or Neurology consult – Consider discussing with the Clinical Study Lead, as needed. – Promptly start IV methylprednisolone 2 to 4 mg/kg/day systemic steroids along with receiving input from Neurology consultant. – If after start of IV methylprednisolone at 2 to 4 mg/kg/day there is no improvement within 2 to 3 days, consider starting another immunosuppressive therapy such as a TNF inhibitor (e.g., infliximab at 5 mg/kg IV, may be repeated at 2 and 6 weeks after initial dose at the discretion of the treating provider or relevant practice guidelines). Caution: It is important to rule out sepsis and refer to infliximab label for general guidance before using infliximab.
1 SCAR terms include Stevens-Johnson Syndrome (SJS), Toxic Epidermal Necrolysis (TEN), Erythema Multiforme, Acute Generalized Exanthematous Pustulosis, Drug Reaction with Eosinophilia and Systemic Symptoms (DRESS) and Drug-induced hypersensitivity syndrome.			
Other-Immune-Mediated Reactions			
Grade	Dose Modifications		Toxicity Management
Any Grade	Note: It is possible that events with an inflammatory or immune mediated mechanism could occur in nearly all organs, some of them are not noted specifically in these guidelines (e.g. immune thrombocytopenia, haemolytic anaemia, uveitis, vasculitis).		
 – Patients should be thoroughly evaluated to rule out any alternative etiology (e.g., disease progression, other medications, or infections). – The Clinical Study Lead may be contacted for immune-mediated reactions not listed in the “specific immune-mediated reactions” section. – Consultation with relevant specialist – Treat accordingly, as per institutional standard.
Grade 1	No dose modifications.		Monitor as clinical indicated.
Grade 2	
 • Hold study drug/study regimen until resolution to ≤Grade 1 or baseline. • If toxicity worsens, then treat as Grade 3 or Grade 4. • Study drug/study regimen can be resumed once event stabilizes to Grade ≤1 after completion of steroid taper. • Consider whether study drug/study regimen should be permanently discontinued in Grade 2 events with high likelihood for morbidity and/or mortality when they do not rapidly improve to Grade <1 upon treatment with systemic steroids 		For Grade 2, 3, or 4 Treat accordingly, as per institutional standard, appropriate clinical practice guidelines, and society guidelines.

	and following full taper.	
Grade 3	Hold study drug/study regimen	
Grade 4	Permanently discontinue study drug/study regimen.	

Infusion-Related Reactions		
Grade	Dose Modifications	Toxicity Management
Any Grade	General guidance.	
 - Manage per institutional standard at the discretion of investigator - Monitor patients for signs and symptoms of infusion-related reactions (e.g., fever and/or shaking chills, flushing and/or itching, alterations in heart rate and blood pressure, dyspnea or chest discomfort, or skin rashes) and anaphylaxis (e.g., generalized urticaria, angioedema, wheezing, hypotension, or tachycardia).
Grade 1 or 2	
For Grade 1 The infusion rate of study drug/study regimen may be decreased by 50% or temporarily interrupted until resolution of the event.
 
For Grade 2
 
 • The infusion rate of study drug/study regimen may be decreased 50% or temporarily interrupted until resolution of the event. • Subsequent infusions may be given at 50% of the initial infusion rate. 	
For Grade 1 or Grade 2:
 
 - Acetaminophen and/or antihistamines may be administered per institutional standard at the discretion of the investigator - Consider premedication per institutional standard or study protocol prior to subsequent doses - Steroids should not be used for routine medication of Grade \leq 2 infusion reactions.
Grade 3 or 4	Permanently discontinue study drug/study regimen	
For Grade 3 or 4:
 
 - Manage severe infusion-related reactions per institutional standard, appropriate clinical practice guidelines, and society guidelines.

Non-immune Mediated Reactions		
Grade	Dose Modification	Toxicity Management
Any Grade	Note: dose modifications are not required for adverse events not deemed to be related to study treatment (i.e. events due to underlying disease) or for laboratory abnormalities not deemed to be clinically significant.	Treat accordingly as per institutional standard
1	No dose modifications.	
2-3	Hold study drug/study regimen until resolution to Grade \leq 1 or baseline	
4	Discontinue Study drug/study regimen (Note for Grade 4 labs, decision to discontinue would be based on accompanying clinical signs/symptoms and as per Investigator's clinical judgment and in consultation with the sponsor)	

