Immune-mediated events can occur in nearly any organ or tissue, therefore, these guidelines may not include all the possible immune-mediated reactions. Investigators are advised to take into consideration the appropriate practice guidelines and other society guidelines (e.g., National Comprehensive Cancer Network (NCCN), European Society of Medical Oncology (ESMO)) in the management of these events. Refer to the section of the table titled "Other -Immune-Mediated Reactions" for general guidance on imAEs not noted in the "Specific Immune-Mediated Reactions" section.

Early identification and management of imAEs is essential to ensure safe use of the study drug. Monitor patients closely for symptoms and signs that may be clinical manifestations of underlying imAEs. Patients with suspected imAEs should be thoroughly evaluated to rule out any alternative etiologies (e.g., disease progression, concomitant medications, infections). In the absence of a clear alternative etiology, all such events should be managed as if they were immune-mediated. Institute medical management promptly, including specialty consultation as appropriate. In general, withhold study drug/study regimen for severe (Grade 3) imAEs. Permanently discontinue study drug/study regimen for life-threatening (Grade 4) imAEs, recurrent severe (Grade 3) imAEs that require systemic immunosuppressive treatment, or an inability to reduce corticosteroid dose to 10 mg or less of prednisone or equivalent per day within 12 weeks of initiating corticosteroids.

Based on the severity of the imAE, durvalumab and/or tremelimumab should be withheld and corticosteroids administered. Upon improvement to Grade ≤ 1 , corticosteroid should be tapered over ≥ 28 days. More potent immunosuppressive agents should be considered for events not responding to systemic steroids. Alternative immunosuppressive agents not listed in this guideline may be considered at the discretion of the investigator based on clinical practice and relevant guidelines. With long-term steroid and other immunosuppressive use, consider the need for glucose monitoring.

Dose modifications of study drug/study regimen should be based on severity of treatment-emergent toxicities graded per NCI CTCAE version in the applicable study protocol.

Considerations for Prophylaxis for Long Term use of Steroids for Patients Receiving Immune Checkpoint Inhibitor Immunotherapy

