Pneumonitis / Interstitial ILD	Any Grade	General guidance	
 - Patients should be thoroughly evaluated to rule out any alternative etiology with similar clinical presentation (e.g. infection, progressive disease) - Monitor patients for signs (e.g. tachypnoea) and symptoms of pneumonitis or ILD (new onset or worsening shortness of breath or cough). Evaluate patients with imaging and pulmonary function tests including other diagnostic procedures as described below - Suspected pneumonitis should be confirmed with radiographic imaging and other infectious and disease-related etiologies excluded, and managed as described below. - Initial work-up may include clinical evaluation, monitoring of oxygenation via pulse oximetry (resting and exertion), laboratory work-up (including clinically relevant culture specimens to rule out infection). and high-resolution computed tomography (CT) scan. - Consider Pulmonary and Infectious Diseases consults.
	Grade 1	No dose modification required. However, consider holding study drug/study regimen dosing as clinically appropriate and during diagnostic work-up for other etiologies	For Grade 1 
 - Monitor and closely follow up in 2-4 days for clinical symptoms, pulse oximetry (resting and exertion) and laboratory work-up and then as clinically indicated
	Grade 2	Hold study drug/study regimen dose until Grade 2 resolution to ≤ Grade 1.	For Grade 2 
 - Monitor symptoms daily and consider hospitalization, as clinically indicated. - Consider Pulmonary and Infectious Diseases Consults. - Promptly start systemic steroids (e.g., prednisone 1 to 2mg/kg/day PO or

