	Grade 2	Hold study drug/study regimen until resolution to \leq Grade 1	
For Grade 2 diarrhea:
 
 - Consider symptomatic treatment including hydration, electrolyte replacement, dietary changes (e.g., American Dietetic Association colitis diet), and loperamide and/or budesonide - Consider further evaluation with imaging study with contrast. - Consider consult of a gastrointestinal (GI) specialist for consideration of further workup. - Promptly start prednisone 1 to 2 mg/kg/day PO or IV equivalent - If no improvement within 3 days despite therapy with 1 to 2 mg/kg IV prednisone equivalent, reconsult GI specialist and, if indicated, promptly start immunosuppressant agent such as infliximab at 5mg/kg IV, may be repeated at 2 and 6 weeks after initial dose at the discretion of the treating provider or relevant practice guidelines. Caution: Important to rule out bowel perforation and refer to infliximab label for general guidance before using infliximab. - If perforation is suspected, consult a surgeon experienced in abdominal surgery immediately without any delay. - Consider, as necessary, discussing with Clinical Study Lead if no resolution to \leq Grade 1 in 3 to 4 days.

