	ALT or AST $> 3 \leq 5$ x ULN or total bilirubin $> 1.5 \leq 3$ x ULN	
 Hold study drug/study regimen dose until ALT or AST ≤ 3 X ULN or total bilirubin, ≤ 1.5 X ULN. Resume study drug/study regimen after completion of steroid taper (<10mg prednisone or equivalent). Permanently discontinue study drug/study regimen for any case meeting Hy's law laboratory criteria (AST or ALT ≥ 3 xULN AND bilirubin ≥ 2 x 	
 Regular and frequent checking of transaminases and total bilirubin (e.g. every 1 to 2 days) until transaminases and total bilirubin elevations improve or resolve. If no resolution to ALT or AST ≤ 3 x ULN or total bilirubin ≤ 1.5 x ULN in 1-2 days, consider, discussing with Clinical Study Lead as needed. If event is persistent (> 2 to 3 days) or worsens, promptly start prednisone 1 to 2mg/kg/day PO or IV equivalent.

PLEASE SEE shaded area immediately below this section to find guidance for management of "Hepatitis (elevated LFTS)" in hepatocellular carcinoma (HCC) patients (or secondary tumor involvement of the liver with abnormal baseline values [BLV]
	
ALT or AST > 5- ≤ 10 x ULN
	
ULN without initial findings of cholestasis (i.e., elevated ALP)) and in the absence of any alternative cause.
 
 Hold study drug/study regimen. Resume study drug/study regimen if elevations downgrade to ALT or AST ≤ 3 x ULN or total bilirubin ≤ 1.5 x ULN after completion of steroid taper (<10 mg prednisone, or equivalent). 	
 Promptly initiate empiric IV methylprednisolone at 1 to 2 mg/kg/day or equivalent Perform Hepatology Consult, abdominal workup, and imaging as appropriate. If still no improvement within 2 to 3 days despite 1 to 2 mg/kg/day methylprednisolone IV or equivalent, promptly start treatment with an additional immunosuppressant (i.e., mycophenolate mofetil 0.5 to 1 g every 12 hours then taper in consultation with hepatology consult or relevant practice guidelines). Discuss with Clinical Study Lead if mycophenolate is not available. Infliximab should NOT be used.

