			
 • If creatinine returns to baseline, resume regular monitoring per study protocol. • If creatinine worsens, depending on the severity, treat as Grade 2, 3, or 4. 
- Consider hydration, electrolyte replacement, and diuretics. as clinically indicated.
 
 - Consider nephrologist consult if not resolved within 14 days, or earlier as clinically indicated
	Grade 2	Hold study drug/study regimen until resolution to Grade \leq 1 or baseline.	
For Grade 2:
 
 - Consider including hydration, electrolyte replacement, and diuretics as clinically indicated. - Follow urine protein/creatinine ratio every 3-7 days - Carefully monitor serum creatinine as clinically warranted. - Consult nephrologist and consider renal biopsy if clinically indicated. - Start prednisone 0.5 – 1 mg/kg/day if other causes are ruled out - If event is persistent beyond 5 days or worsens, increase to prednisone up to 2 mg/kg/day PO or IV equivalent. - If event is not responsive within 5 days or worsens despite prednisone at 1 to 2 mg/kg/day PO or IV equivalent, consider additional workup. When event returns to baseline, resume study drug/study regimen and routine serum creatinine monitoring per study protocol.
	Grade 3 or 4	Permanently discontinue study drug/study regimen	
For Grade 3 or 4:
 
 - Carefully monitor serum creatinine daily. - Follow urine protein/creatinine ratio every 3-7 days - Consult nephrologist and consider renal biopsy if clinically indicated. - Promptly start prednisone 1 to 2 mg/kg/day PO or IV equivalent. - If event is not responsive within 3 to 5 days of steroids or worsens despite prednisone at 1 to 2 mg/kg/day or IV equivalent, consider additional workup and prompt treatment with an immunosuppressant.
Rash or Dermatitis (including Pemphigoid)	Any Grade (refer to NCI CTCAE v 4.03 for definition of severity / grade depending on type of skin rash)	General guidance	
For Any Grade:
 
 - Patients should be thoroughly evaluated to rule out any alternative etiology. - Monitor for signs and symptoms of dermatitis (rash and pruritus). - HOLD STUDY DRUG IF GRADE 3 PEMPHIGOID OR SEVERE CUTANEOUS ADVERSE REACTION (SCAR)¹ IS SUSPECTED. - PERMANENTLY DISCONTINUE STUDY DRUG IF SCAR OR GRADE 3 PEMPHIGOID IS CONFIRMED.

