	Grade 1	No dose modifications.	
For Grade 1:
 
 - Consider symptomatic treatment including oral antipruritics (e.g., diphenhydramine or hydroxyzine) and topical therapy (e.g., emollient, lotion, or institutional standard).

	Grade 2	For persistent (> 1 week) Grade 2 events, hold scheduled study drug/study regimen until resolution to ≤ Grade 1 or baseline 
 If toxicity improves to Grade ≤ 1 or baseline, then resume drug/study regimen after completion of steroid taper (<10 mg prednisone, or equivalent). 	For Grade 2: 
 Consider Dermatology consult and skin biopsy, as indicated. Consider symptomatic treatment including oral antipruritics (e.g., diphenhydramine or hydroxyzine) and topical therapy. Consider moderate-strength topical steroid If no improvement of rash/skin lesions occurs within 1 week or is worsening despite symptomatic treatment and/or use of moderate strength topical steroid, consider discussing with Clinical Study Lead, as needed, and promptly start systemic steroids prednisone 1 to 2 mg/kg/day PO or IV equivalent.
	Grade 3	Grade 3: 
 Hold study drug/study regimen until resolution to Grade ≤ 1 or baseline If toxicity improves to Grade ≤ 1 or baseline, then resume study drug/study regimen after completion of steroid taper (<10 mg prednisone, or equivalent). 	For Grade 3 
 Reconsult a dermatologist. Consider skin biopsy (preferably more than 1) as clinically feasible. Promptly initiate empiric IV methylprednisolone 1 to 2 mg/kg/day or equivalent. Consider hospitalization. Monitor the extent of rash [Rule of Nines]. Consider, as necessary, discussing with Clinical Study Lead.
	Grade 4	For Grade 4 Permanently discontinue study drug/study regimen	For Grade 4 
 Reconsult a dermatologist. Consider skin biopsy (preferably more than 1) as clinically feasible. Promptly initiate empiric IV methylprednisolone 1 to 2 mg/kg/day or equivalent. Consider hospitalization. Monitor the extent of rash [Rule of Nines]. Consider, as necessary, discussing with Clinical Study Lead.

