	Grade 2	
 • Hold study drug/study regimen dose until resolution to Grade ≤ 1. • Permanently discontinue study drug/study regimen if it does not resolve to Grade ≤ 1 within 30 days or if there are signs of respiratory insufficiency. 	
For Grade 2
 
 - Monitor symptoms daily and consider hospitalization. - Consider Rheumatology or Neurology consult, and initiate evaluation. - Consider, as necessary, discussing with the Clinical Study Lead. - If clinical course is rapidly progressive (particularly if difficulty breathing and/or trouble swallowing), promptly start IV methylprednisolone 2 to 4 mg/kg/day systemic steroids along with receiving input from Neurology consultant - If clinical course is not rapidly progressive, start systemic steroids (e.g., prednisone 1 to 2 mg/kg/day PO or IV equivalent); if no improvement within 2 to 3 days, continue additional work up and start treatment with IV methylprednisolone 2 to 4 mg/kg/day - If after start of IV methylprednisolone at 2 to 4 mg/kg/day there is no improvement within 3 days, consider additional immunosuppressive therapy such as TNF inhibitors (e.g., infliximab, IVIG or plasmapheresis, or other therapies based on the discretion of the treating specialist consultant or relevant practice guideline. Caution: It is important to rule out sepsis and refer to infliximab label for general guidance before using infliximab.

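### Section 9.3.1 ends the durvalumab hold at Grade ≤1 after Grade 2 pneumonitis, colitis, nephritis or myositis, just as the steroid taper begins, while comparable rows require the taper to be finished

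*Combined protocol and SAP*

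**What the plan says.** The General Considerations in Section 9.3.1 state that, once an immune-mediated event improves to Grade ≤1, "corticosteroid should be tapered over ≥ 28 days".

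Four Grade 2 rows prescribe systemic steroids and then end the durvalumab hold without mentioning that taper:

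- Pneumonitis/ILD: "Hold study drug/study regimen dose until Grade 2 resolution to ≤ Grade 1".
- Diarrhea/colitis: "Hold study drug/study regimen until resolution to \leq Grade 1".
- Myositis: "Hold study drug/study regimen dose until resolution to Grade ≤ 1", with permanent discontinuation if this is not reached within 30 days or if there is respiratory insufficiency.
- Nephritis: the dose column holds until Grade ≤1 or baseline, and the management column adds "When event returns to baseline, resume study drug/study regimen and routine serum creatinine monitoring per study protocol". Steroids are given here only if other causes have been ruled out.

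Three comparable rows set a stricter condition:

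- Hepatitis with ALT/AST above 3 and up to 5 × ULN: "Resume study drug/study regimen after completion of steroid taper (<10mg prednisone or equivalent").
- Rash, Grade 2: "then resume drug/study regimen after completion of steroid taper (<10 mg prednisone, or equivalent").
- Default row for immune-mediated events not listed by name, Grade 2: "Study drug/study regimen can be resumed once event stabilizes to Grade ≤1 after completion of steroid taper".

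**The concern.** The taper starts at the same improvement that ends the hold. Read as written, the next infusion may fall due while the patient is still on a substantial steroid dose. A Grade ≤1 reading at that moment may reflect suppression by the steroid rather than resolution. That is clinical reasoning; the documents give no rate for it.

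The table also applies two standards to patients on similar doses. Grade 2 rash that needs prednisone 1–2 mg/kg/day must wait for the end of the taper, while Grade 2 pneumonitis on the same dose need not. Colitis differs within itself: Grade 3 on durvalumab monotherapy requires the taper to be complete and Grade 2 does not. The protocol offers no reason for the difference. Safety is the primary objective (Section 1.1), so the restart rule matters both to patients and to the interpretation of recurrent events.

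**Working it through.** **Text comparison (Section 9.3.1)**

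| Row | Steroid | Hold ends at | Taper complete? |
|---|---|---|---|
| Pneumonitis, Grade 2 | 1–2 mg/kg/day | Grade ≤1 | Not required |
| Colitis, Grade 2 | 1–2 mg/kg/day | Grade ≤1 | Not required |
| Nephritis, Grade 2 | 0.5–1 mg/kg/day, up to 2, if other causes are ruled out | Grade ≤1 or baseline | Not required |
| Myositis, Grade 2 | 1–2 mg/kg/day if not rapidly progressive | Grade ≤1 | Not required |
| Hepatitis, ALT/AST >3–5 × ULN | 1–2 mg/kg/day if persistent or worse | ALT/AST ≤3 × ULN or bilirubin ≤1.5 × ULN | Required, <10 mg |
| Rash, Grade 2 | 1–2 mg/kg/day if no improvement | Grade ≤1 or baseline | Required, <10 mg |
| Default row, Grade 2 | Institutional standard | Grade ≤1 | Required |

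**Search for a rule elsewhere that closes the gap**

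- Section 9.3.1, 12-week rule: permanent discontinuation if the dose cannot be brought to 10 mg/day or less. It does not govern restart before then.
- Section 8.4.2: bars steroids above 10 mg/day but exempts those given for drug-related events.
- Section 9.1.2: a need for steroids ends immunizations; durvalumab is not named.
- Section 12.1(5): allows removal if a related Grade 2 event has not reached Grade 1 by the next treatment. There is no steroid test.
- Section 14.1: a related SAE, or a second case of the same probably or definitely related Grade 2 event, halts injections and enrollment. Infusions are not named, and one non-serious Grade 2 event does not trigger it.

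None of these sets a steroid dose for restart.

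**Dose at the next infusion**

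The plan states no figure for this, so there is none to reproduce. Inputs: 75 kg reference weight (Section 2.10.4); infusions every 28 days ±7 (Section 8.2); minimum taper 28 days (Section 9.3.1). Assumptions not in the documents: the taper is linear to zero over exactly 28 days and starts *r* days after the last infusion.

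Starting dose *D*: 75 × 0.5 = 37.5; 75 × 1 = 75; 75 × 2 = 150 mg/day.

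Dose on day *d* = *D* × (1 − (*d* − *r*)/28). On day 28 this is *D* × *r*/28, which exceeds 10 mg when *r* > 280/*D*. On day 35 it is *D* × (*r* − 7)/28, which exceeds 10 mg when *r* > 7 + 280/*D*.

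| *D* (mg/day) | Day 28, *r* = 14 | Day 35, *r* = 14 | >10 mg on day 28 if *r* exceeds | >10 mg on day 35 if *r* exceeds |
|---|---|---|---|---|
| 37.5 | 18.8 mg | 9.4 mg | 7.5 days | 14.5 days |
| 75 | 37.5 mg | 18.8 mg | 3.7 days | 10.7 days |
| 150 | 75 mg | 37.5 mg | 1.9 days | 8.9 days |

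At 1–2 mg/kg the visit window absorbs the gap only if Grade ≤1 is reached within about 9–11 days of the last infusion. At 0.5 mg/kg it does so up to about 14 days. Under the same model, a taper longer than 28 days leaves higher doses.

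**Exposure**

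24 patients randomized 1:1 (Section 4.6) give 12 on durvalumab. Each receives at most four infusions (Section 8.7), and the first cannot be a restart: 12 × (4 − 1) = 36 at most.

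**The case against.** The strongest reply is that the table guides judgement and does not authorize re-dosing. Section 9.3.1 presents it as a recommendation, and Section 13.1.4.2 describes it as an aid to the investigator's judgement. Section 9.2 asks for a benefit-risk assessment before further durvalumab. Only the nephritis row actually says to resume; the others state what the hold must wait for. Related patients may be removed under 12.1(5) or 12.1(8), myositis has its 30-day limit, and toxicities are reviewed at a weekly Phase 1 meeting (Section 14.3). No text says that all organs must share one restart rule.

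This stands as far as it goes. These are real, partial safeguards, and an investigator may hold longer. But the table is the protocol's only written restart standard, and none of the safeguards supplies the missing steroid condition.

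On the other side, a reader might infer several stronger points that the documents do not support:

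- *That the cited society guidelines also lack a threshold.* Their content is not in the documents.
- *That the 12-week rule can never act before the last infusion.* Days 85 to 169 are 84 days, exactly 12 weeks, so this holds on schedule. A held patient may run late: an event on Day 86 reaches 12 weeks on Day 170, before the last window closes on Day 176.
- *That Grade 2 neuropathy and Grade 3 myositis are equally clear cases.* Neuropathy steroids are optional. A related Grade 3 myositis also meets removal criterion 12.1(6) and, if probably or definitely related, the Section 14.1 halt.
- *That a restart re-exposes the patient to the full combination.* Under Section 9.1.2 a need for steroids ends vaccination, so the restart would be durvalumab without further vaccine.

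**Conclusion.** The inconsistency is real, and correcting it is a worthwhile, low-cost safety improvement. After four Grade 2 events treated with steroids (nephritis conditionally), the written hold ends when the taper is only starting, and the protocol's own text sets no steroid threshold for restart. Comparable rows do set one.

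The illustrative size is about 38–75 mg/day of prednisone at the next scheduled infusion and 19–38 mg/day at the end of the window. It rests on a 75 kg patient on 1–2 mg/kg, a linear 28-day taper and Grade ≤1 reached 14 days after the last infusion; the result moves with *r*, as shown above. At most 36 infusions in about 12 patients could be affected. The true number is probably far lower, since it requires one of these events, steroid treatment and timely improvement, but no incidence is given. The finding does not show that patients would in fact be re-dosed on high-dose steroids, only that the written criterion does not prevent it.

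**What to change.** Add one sentence to Section 9.3.1: after any immune-mediated event treated with systemic steroids, durvalumab restarts only when the event is at Grade ≤1 (or baseline) and the taper is finished, meaning prednisone below 10 mg/day or equivalent. Keep the exception in the Grade 2–4 endocrinopathy row for patients on replacement steroids, such as those with adrenal insufficiency.

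No patients or tests are added. The cost is that some of the at most four infusions are delayed or missed. Under the same taper assumptions, the delay past day 28 is *r* − 280/*D*. From 75–150 mg/day that is about 3–5 days for *r* = 7 (inside the window), 10–12 days for *r* = 14 and 17–19 days for *r* = 21. From 37.5 mg/day it is none, 6.5 and 13.5 days. In affected patients this slightly lowers durvalumab exposure behind the Day 113 and Day 169 between-arm comparison (Section 15.2.1), chiefly at Day 169, because the earliest possible restart infusion is the one due on Day 113.
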